6.10.2 Blood/Bone Marrow

Monitored treatment related toxicity associated with blood and bone marrow function will include anemia, leukocytopenia, thrombocytopenia, and myelodysplasia. The consequences of blood and bone marrow toxicity should all be graded according to the Common Terminology Criteria For Adverse Events (CTCAE).

6.10.3 Constitutional Symptoms

Monitored treatment related toxicity associated with constitutional function will include fatigue, fever, and weight loss. The consequences of constitutional toxicity should all be graded according to the Common Terminology Criteria For Adverse Events (CTCAE).

#### 6.10.4 Skin

Monitored treatment related toxicity associated with skin function will include fibrosis, rash (desquamation), ulceration, and telangiectasia. The consequences of skin toxicity should all be graded according to the Common Terminology Criteria For Adverse Events (CTCAE).

#### 6.10.5 Gastro-intestinal

Monitored treatment related toxicity associated with gastrointestinal function will include colitis, dehydration, diarrhea, enteritis, fistula, nausea, vomiting, obstruction, proctitis, fecal incontinence, stricture/stenosis, hemorrhage, and ulcer. The consequences of gastro-intestinal toxicity should all be graded according to the Common Terminology Criteria For Adverse Events (CTCAE).

6.10.6 Renal/Genitourinary

Monitored treatment related toxicity associated with renal and genito-urinary function will include cystitis, fistula, urinary incontinence, urinary obstruction, hemorrhage, and urinary retention. The consequences of renal/genitourinary toxicity should all be graded according to the Common Terminology Criteria For Adverse Events (CTCAE).

6.10.7 Quality of Life and Other Toxicities

Other treatment related toxicity attributed to the therapy will be captured, recorded and the consequences of should all be graded according to the Common Terminology Criteria For Adverse Events (CTCAE). VAS, BPI, FACT-G and EQ-5D

#### 6.11 Serious Adverse Event Reporting

6.11.1 ERGO

Electronic Research Grant Organizer (ERGO) constitutes a mechanism for reporting serious adverse events to the UTSW IRB for reporting purposes.

Any adverse event equivalent to CTCAE V.3 grade 3, 4, or 5 or which precipitates hospitalization or prolongs an existing hospitalization must be reported regardless of designation (expected or unexpected) along with the attribution. This includes all deaths that occur within 30 days after the patient was discontinued from the study regardless of attribution AND any events that occur beyond 30 days and are considered probably related to treatment.

Participating sub-sites must file an SAE report (the CRF plus information describing the event, the grade, and the attribution) within 48 hours of the investigator's awareness of the occurrence of the event.

Attribution of an event can be categorized as:

- Not Related
- Possibly Related
- Likely Related

Adverse events (below grade 3) do not need to be submitted immediately. Rather, they should be documented in the Adverse Events CRF along with a brief description of the event, grade, and attribution).

All SAE reports should be made via FAX transmission to:

#### Department of Radiation Oncology Clinical Research Office The University of Texas Southwestern Medical Center Attention: [name], Project Manager [contact]

#### 7.0 Drug Therapy:

Chemotherapy will be held 1 week prior to radiation and may be continued one week after treatment.

#### 8.0 Surgery:

8.1 Vertebroplasty

Vertebroplasty will be performed within one month of start of radiation therapy in the standard angiography suite or in the operating room depending on individual patient needs. C-arm fluoroscopy will be utilized for localization and visualization throughout the procedure. All patients undergo continuous physiologic monitoring and observation by anesthesia provider. In most instances the procedure may be completed using conscious sedation with a combination of a short acting narcotic and benzodiazepine. Local anesthesia with lidocaine or bupivicaine is also utilized.

The patient will be positioned prone on the operating table, prepped and draped in the usual sterile fashion. Under fluoroscopic guidance, the pedicle of the involved vertebral level is localized. The skin, soft tissue and periosteum are anesthetized. A standard bone biopsy needle with an outer cannula and a central stylet is advanced under fluoroscopic guidance into the vertebral body via the pedicle. The stylet is removed and the polymethyl methacrylate (PMMA) mixture is injected into the vertebral body through the cannula under continuous fluoroscopy. Careful attention to any extravasation is noted. After adequate vertebral body fill, the cannula is withdrawn and a sterile dressing applied to the puncture site.

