#### Exclusion:

- Patients who have been non-ambulatory for more than 7 days
- Patients with compression fractures

- Spine instability requiring fixation
- Patients with paraspinal extension
- Patients with bony fragments
- Planned systemic treatment within one week after treatment.
- Absence of pathological diagnosis of cancer
- Chemotherapy within one week of treatment
- Patients with Multiple Myeloma, Lymphoma, or Plasmacytoma
- Patient suffered from unstable angina and/or congestive heart failure requiring hospitalization within the last 6 months
- Patient had a transmural myocardial infarction within the last 6 months
- Patient has an acute bacterial or fungal infection requiring intravenous antibiotics at the time of registration
- Patient has hepatic insufficiency resulting in clinical jaundice and/or coagulation defects
- PT is not within normal limits or planned and feasible to be corrected to normal limits prior to vertebroplasy
- PTT is not within normal limits or planned and feasible to be corrected to normal limits prior to vertebroplasy
- Platelet count is < 50,000
- History of significant psychiatric illness

Vertebroplasty may not be possible for certain patients due to tumor location or safety. In such cases, patients will omit the vertebroplasty but receive all other protocol care and follow-up. Visual Analog Scoring

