#### 1.3 Vertebroplasty:

Currently, the management of metastatic spinal tumors in the neurologically intact patient includes radiotherapy alone or a combination of surgery and radiotherapy for tumor suppression, pain reduction, and spinal stabilization[17]. Extensive surgical treatment is often limited by a patient's poor general condition, the multifocal nature of the disease, or the patient's short life expectancy. Radiation therapy alone does not impart early spinal stability and, frequently, patients progress to develop further vertebral body height loss or progressive deformity[18]. Percutaneous vertebral augmentation procedures can be effective in preventing further vertebral body collapse and in improving pain relief.

Percutaneous Vertebroplasty (PV) is a minimally invasive fluoroscopically guided procedure aimed at augmenting the vertebral body by injection of polymethyl methacrylate (PMMA) Initially developed in France in the late 1980's to treat aggressive vertebral angiomas, vertebroplasty has gained widespread acceptance worldwide[19]. In the United States, it is predominantly used to treat osteoporotic compression fractures. Percutaneous kyphoplasty is a modification of PV. It involves the percutaneous placement of balloons into the vertebral body, followed by an inflation/deflation sequence to create a cavity prior to the cement injection. The PK procedure may restore VB height and reduce kyphotic angulation prior to PMMA injection[20]. Vertebroplasty has been shown to be effective in controlling pain secondary to compression fractures in over 90% of patients in prospective studies[21]. Significant improvement in quality of life and decreased oral analgesic usage has also been shown. Although not widely used in the United States, vertebroplasty for metastatic spine disease has been shown in multiple studies to be effective in controlling pain and improving quality of life. In one study, 97% of patients experienced decrease in pain within 48 hours of the procedure. In another study 73% of patients decreased their oral analgesic dose by 50% or more[22-25].

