methacrylate and is indicated in patients with pain from benign and malignant compression. Since radiation to the spine contributes to osteopenia that could lead to destabilization or fracture, vertebroplasty may prevent this late radiation effect. Unfortunately, vertebroplasty may not be technically possible in certain patients due to inability to safely inject the cement. For example, in some cervical spine locations, the vertebral arteries prohibit an approach through the pedicles. Such levels, however, are less likely to undergo post radiation collapse. As such, if it is not technically feasible to perform vertebroplasty, patients may still benefit from SBRT.

This study proposes combining stereotactic body radiation with vertebroplasty to provide both durable local tumor control and pain control while preventing fracture, spinal destabilization, or spinal cord compression.

The hypothesis of this study is stereotactic radiation treatments combined with vertebroplasty will increase pain relief at one month to 80% compared with conventional historical controls of approximately 50% in the setting of patients with no prior radiation treatments and for the group of patients with a history of prior radiation stereotactic radiation combined with vertebroplasty will increase the pain relief at one month to 75% compared with conventional historical retreatment control of approximately 35%.

1.5 Quality of Life (QOL) measurements:

Patients with spinal metastasis have unique clinical considerations. Focal treatments such as radiation are often used to palliate or prevent symptoms such as pain, decreased mobility, fracture, and spinal cord compression. QOL measurements have very important clinical implications since our therapy is directed at improving subjective symptoms such as pain. Improved understanding of patient's symptoms and perceptions of treatment will guide what treatments are most advantageous in the future.

1.5.1 Visual Analogue Scoring System (VAS):

The VAS is a simple measure of pain in 11 scales (0-10). In the study comparing the reliability and validity of several measures of pain intensity, the composites of 0-10 ratings was useful practically when maximal reliability is necessary in studies with relatively small sample sizes or in clinical settings where monitoring of changes in pain intensity in individuals is needed[34].

1.5.2 Brief Pain Inventory (BPI):

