#### 2.0 Objectives:

2.1 Primary: To determine the efficacy of stereotactic body radiation for spinal metastasis in reduction of pain at one month. Both partial and complete response will be measured by the visual analogue system (VAS). Partial relief equals an improvement of 2 points on the VAS and complete pain response is defined by a score of 0-1 on the VAS with no increase in narcotic requirement.

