#### **11.2 Follow-up Schedule**

- **11.2.1** Initial follow-up visit at 2 weeks then 1, 3 and 6 months from start of treatment.
- **11.2.2** VAS will be measured at 2 weeks, 1, 3, and 6 months and then every 6 months for 3 years by research staff. VAS will be measured on the day of treatment and weekly there after for 5 weeks by patient diary.
- **11.2.3** BPI, Fact-G, and EQ-5D will be done at baseline, 1, 3, 6, and 12 months post therapy.
- **11.2.4** After initial follow-up visits, follow-up will be done at 6 month intervals post therapy for 3 years.
- **11.2.5** MRI at baseline, 1, 3, 6 and then every 6 months for three years. These MRI are to be done of the treated level and a complete whole spine MRI will be done when clinically indicated based on pain or other new neurological symptom.

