## Please note that this study will not be using separate toxicity scales for acute and late radiation adverse events.

#### 11.4 Measurement of Pain Response

- **11.4.1** Pain as the primary endpoint of the study will be assessed by VAS at 1 month by research staff.
- **11.4.2** Pain will also be assessed by VAS at 2 weeks, 1, 3, and 6 months and then every 6 months for 3 years post therapy by research staff. A patient pain diary of maximum VAS of treated spine recorded on the same day of radiation treatment and then weekly for 5 weeks following radiation treatment.
  - **11.4.2.1** Response to pain will be scored as Complete Response (CR), Partial Response (PR), or other.
  - **11.4.2.2** Complete response (CR): defined as a score of 0 on the VAS at the treated site with no increase in narcotic requirements
  - **11.4.2.3** Partial response (PR): defined as an improvement of at least two points on the VAS with no increase in narcotic requirement.
  - **11.4.2.4** Other will include people with stable pain, increasing narcotic requirements, and progressive pain

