## Appendix I

## **STUDY PARAMETER TABLE**

	PreTreatment		During Treatment			Follow-Up (months after therapy)				
	Within 30 days of study entry		After last treatment	1	3	6	Every 6 months for three years			
Confirmation of Pathology	Х									
History/physical	Х	Х	Х	Х	Х	Х	Х			
Performance Status	Х			Х	Х	Х	Х			
MRI spine*	$X^1$			X1	X1	X 	X 			
CT spine*	$X^1$			$X^1$	$X^1$	X 	X 			
BUN, creatinine, CBC w/ platelets, PT/PTT INR	Х									
Informed consent	Х									
Tumor response evaluation	Х			Х	Х	Х	Х			
VAS at treated Site	Х		Х	Х	Х	Х	Х			
Adverse event evaluation		Х	Х	Х	Х	Х	X			
QOL Studies	Х		Х	Х	Х	Х	X			
(BPI, Fact-G, EQ-5D) Vertebroplasty	X	X 	1	x	x	x	(12 months only)			

 $*X^1$ : Per physician's discretion  $X^2$  : within one month of start of radiation treatment.

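### The one-month response rate mixes SBRT alone with SBRT plus vertebroplasty at varying intervals, so rejecting H0 cannot support the SBRT-only claim in objective 2.1

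*Combined protocol and SAP*

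**What the plan says.** **Which treatment the test evaluates.** Objective 2.1 reads "To determine the efficacy of stereotactic body radiation for spinal metastasis in reduction of pain at one month". The design tables in Sections 13.1 and 13.2 likewise label P1 (0.80 and 0.75) as the response probability of stereotactic radiation. The title names both SBRT and vertebroplasty. Section 1.4 states, for patients without prior radiation, that "stereotactic radiation treatments combined with vertebroplasty will increase pain relief at one month to 80" per cent, and sets 75% for the combination in retreated patients.

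**When vertebroplasty happens.** Section 8.1 says "Vertebroplasty will be performed within one month of start of radiation therapy", and the Appendix I footnote repeats "within one month of start of radiation treatment". Neither states its order relative to radiation or to the primary VAS. Under footnote 1 of the schema, where the procedure is not possible, "patients will omit the vertebroplasty but receive all other protocol care and follow-up".

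**When pain is read.** Section 11.4.1 says "Pain as the primary endpoint of the study will be assessed by VAS at 1 month by research staff". Section 11.2.1 sets the clock: "Initial follow-up visit at 2 weeks then 1, 3 and 6 months from start of treatment". Appendix I heads its follow-up columns as months following therapy. No visit window is given.

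**What the plan expects of each component.** Section 1.3 cites a study in which "97% of patients experienced decrease in pain within 48 hours of the procedure". Section 1.4 cites about 80% one-month pain response for stereotactic radiation. The historical rates, 50% and 35%, come from conventional radiation.

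**Analysis.** Section 13 has no rule for late or omitted vertebroplasty and no breakdown by its status or timing.

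**The concern.** The protocol gives one test two meanings. Read through 2.1 and the P1 labels, rejecting H0 says that SBRT relieves pain better than conventional radiation. Read through the title and 1.4, it says that SBRT with vertebroplasty does. The plan's own background presents vertebroplasty as a fast and effective pain treatment, so the difference is not merely one of wording: the procedure could supply the responses that carry the test.

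The timing rules add to this. In one patient the VAS may come weeks after the procedure. In another it may come days after, when Section 1.3 says procedural back pain can occur. If the visit is early, it may come before the procedure. Some patients never have it. All count alike among the 29 and the 13. At stake is whether a positive result may be reported as SBRT efficacy, and what a follow-on trial would then be built to test.

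**Working it through.** **Step 1. Reproduce the designs.** With b the binomial probability, the chance of rejecting H0 at true rate p is

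R(p) = sum over x from r1+1 to n1 of b(x; n1, p) × P(Bin(n − n1, p) ≥ r + 1 − x).

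- Single fraction (n1 = 9, r1 = 5, n = 29, r = 18): R(0.50) = 0.048 and R(0.80) = 0.905. Early termination at p0 is 0.746, so the expected size is 9 + 0.254 × 20 = 14.08, as stated.
- Five fractions (6, 2, 13, 7): R(0.35) = 0.043 and R(0.75) = 0.905. Early termination at p0 is 0.647, so the expected size is 6 + 0.353 × 7 = 8.47, as stated.

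The sample-size arithmetic is correct. The problem is what p stands for.

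**Step 2. Set the clocks side by side** (one month taken as 30 days).

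- Clock from start of treatment (11.2.1): the last permitted day for vertebroplasty and the nominal VAS day coincide at day 30. The procedure falls on or before the nominal VAS day. It can follow the reading only if the visit is early or the two share a day, which the missing window allows.
- Clock following therapy (Appendix I), single fraction: the same.
- Clock following therapy, five fractions: Section 6.1.2 allows up to 7 days between fractions, so the last can be on day 4 × 7 = 28. The VAS is then at about day 28 + 30 = 58, and vertebroplasty within its window always comes first.

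The interval from procedure to VAS therefore varies, and omission is also permitted.

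**Step 3. How far vertebroplasty alone could carry the test.** Assume SBRT gives only the historical rate p0, a share v = 0.75 has vertebroplasty before the VAS, and it converts a fraction q of those who would not otherwise respond. Then p = p0 + (1 − p0) × v × q. The documents give neither v nor q; both are assumptions.

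| q | p, single fraction | P(reject H0) | p, five fractions | P(reject H0) |
|---|---|---|---|---|
| 0.25 | 0.50 + 0.50 × 0.1875 = 0.594 | 0.24 | 0.35 + 0.65 × 0.1875 = 0.472 | 0.21 |
| 0.50 | 0.50 + 0.50 × 0.375 = 0.688 | 0.58 | 0.35 + 0.65 × 0.375 = 0.594 | 0.53 |
| 0.75 | 0.50 + 0.50 × 0.5625 = 0.781 | 0.87 | 0.35 + 0.65 × 0.5625 = 0.716 | 0.85 |

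Even at v = 0.25 and q = 0.25 the rejection probabilities are 0.089 and 0.080, above 0.05.

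**Step 4. Readings before vertebroplasty.** Assume the combination gives 0.80, SBRT alone gives s, and a share f = 0.10 of readings comes first. Then p = f × s + (1 − f) × 0.80. In the single-fraction group, s = 0.50 gives p = 0.77 and power 0.85; s = 0.70 gives p = 0.79 and power 0.89; s = 0.80, the figure in Section 1.4, gives p = 0.80 and power 0.905, so nothing is lost.

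**The case against.** The strongest reply is that this is a pragmatic combination trial. Section 13 defines p neutrally as a pain response rate and rejection as grounds for further study of the test treatment. Omission of vertebroplasty is disclosed and explained. Under the title and 1.4, a response above p0 to which vertebroplasty contributes is the effect sought, so the probabilities in Step 3 are power, not error. No single-arm trial of a combination can separate its components, and fixing the order of procedure and VAS would not do so either. All of this stands, and it limits the point to the claim made for SBRT alone. It does not remove the point, because 2.1 and the P1 labels make that claim.

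A reader might go further and infer that vertebroplasty is planned on either side of the primary VAS. The documents do not say this: the window ends on the nominal VAS day. In Appendix I the procedure's mark also appears to sit in the during-treatment position, although the table is too broken in extraction to settle it.

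A reader might also infer that the endpoint measures neither treatment. It measures the combination in patients whose procedure came before the VAS and SBRT alone in those who omitted it; the fault is that the group rate mixes them undefined.

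Finally, a reader might infer a serious loss of power. Single-fraction power of 0.44 would need half of the readings to precede the procedure and SBRT alone to give only 50%. The documents support neither, and at their own 80% there is no loss.

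The plan also collects VAS at 2 weeks and a weekly diary for 5 weeks, so readings around the procedure will exist. What is missing is any planned use of them.

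**Conclusion.** The point holds as a contradiction over which treatment the primary test evaluates, made worse by an unsettled clock and an unrecorded order of procedure and VAS. It should be fixed. The contradiction between 2.1 with the P1 labels and the title with 1.4 needs no assumption.

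Its possible size does. If SBRT adds nothing over the historical rates and 75% have vertebroplasty before the VAS, a positive result arises with probability 0.24 to 0.87 (single fraction) and 0.21 to 0.85 (five fractions) over the assumed conversion range. Those figures are false-positive rates for an SBRT-only claim and for no other. The 97% in Section 1.3 is any decrease in pain, not a 2-point response, so it does not fix the conversion rate.

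The reverse ambiguity matters as well: if SBRT alone gives about 80%, H0 is rejected with probability 0.905 without any vertebroplasty, so a positive result does not show that the procedure added anything. Loss of power from early readings is secondary. The sample sizes and decision rules need no change on this account.

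**What to change.** 1. Make objective 2.1, the P1 labels in Sections 13.1 and 13.2, and the stated meaning of rejecting H0 name the strategy tested: SBRT with vertebroplasty where feasible. This agrees with the title and Section 1.4.
2. Reconcile 8.1, 11.2.1, 11.4.1 and Appendix I on the clock and window of the one-month VAS and on its order relative to vertebroplasty. The clinical timing is for the sponsor to choose.
3. Record the vertebroplasty date for each treated level, or that it was not done and why. Next to the primary result, report one-month response by vertebroplasty status and timing, as a descriptive table without testing.

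The cost is protocol wording, one data field and one table, with no added patients or visits. The price is a narrower claim for SBRT itself and slightly less freedom in scheduling.

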#### 9.0 Other Therapy:

#### 9.1 Permitted Supportive Therapy

All supportive therapy for optimal medical care will be given during the study period at the discretion of the attending physician(s) within the parameters of the protocol and documented on each site's source documents as concomitant medication.

- 9.1.1 Antiemetics
- 9.1.2 Anticoagulants
- 9.1.3 Antidiarrheals
- 9.1.4 Analgesics
- 9.1.5 Hematopoietic Growth Factors
- 9.1.6 Herbal products
- 9.1.7 Nutritional supplementation

#### **10.0 TISSUE/SPECIMEN SUBMISSION**

## 10.1 Specimen Collection For Central Review For Eligibility

Central review of pathology is not required for entry on to this study.

#### **11.0 PATIENT ASSESSMENTS**

11.1 Study Parameters: See Appendix II.

